8.3.2 Direct access to source data and documents

The sponsor will monitor the conduct of the trial by regular on-site monitoring visits and in-house data quality review. The frequency of on-site monitoring will be determined by assessing all characteristics of the trial, including its nature, objective, methodology and the degree of any deviations of the intervention from normal clinical practice.

The Investigator /institution will allow on-site trial-related monitoring, audits, IRB / IEC review and regulatory inspections. Direct access must be provided to the CRF and all source documents/data, including progress notes, copies of laboratory and medical test results, which must be available at all times for review by the CRA, auditor and regulatory inspector (e.g. FDA). The CRA and auditor may review all CRFs and informed consents. The accuracy of the data will be verified by direct comparison with the source documents described in [Section 8.3.1](#). The sponsor will also monitor compliance with the protocol and ICH GCP.

8.3.3 Storage period of records

Trial site(s):

The trial site(s) must retain the source and essential documents (including ISF) according to the national or local requirements (whatever is longer) valid at the time of the end of the trial.

Sponsor:

The sponsor must retain the essential documents according to the sponsor's SOPs.

8.4 EXPEDITED REPORTING OF ADVERSE EVENTS

BI is responsible to fulfil their legal regulatory reporting obligation and in accordance to the requirements defined in this CTP.

8.5 STATEMENT OF CONFIDENTIALITY AND PATIENT PRIVACY

Individual subject data obtained as a result of this trial is considered confidential and disclosure to third parties is prohibited with the exceptions noted below. Subject privacy will be ensured by using subject identification code numbers.

Data protection and data security measures are implemented for the collection, storage and processing of subject data in accordance with the principles 6 and 12 of the WHO GCP handbook.

Treatment data may be given to the subject's personal physician or to other appropriate medical personnel responsible for the subject's welfare. Data generated as a result of the trial need to be available for inspection on request by the participating physicians, the sponsor's representatives, by the IRB / IEC and the regulatory authorities.

8.5.1 Collection, storage and future use of biological samples and corresponding data

Measures are in place to comply with the applicable rules for the collection, storage and future use of biological samples from clinical trial participants and the corresponding data, in particular

- A Quality Management System has been implemented to ensure the adherence with the Principles of Good Clinical Practice as outlined in 'Note For Guidance On Good Clinical Practice' (CPMP/ICH/135/95)
- The BI-internal facilities storing and analysing biological samples and data from clinical trial participants as well as the laboratories' activities for clinical trials sponsored by Boehringer Ingelheim are regularly audited. The analytical groups and the banking facility are therefore assessed to be qualified for the storage and use of biological samples and data collected in clinical trials.
- Samples and data are used only if an appropriate informed consent is available.

8.6 TRIAL MILESTONES

The **start of the trial** is defined as the date of the enrolment of the first subject in the whole trial.

The **end of the trial** is defined as the date of the last visit of the last subject in the whole trial (“Last Patient Out”). The “**Last Patient Drug Discontinuation**” (LPDD) date is defined as the date on which the last patient at an individual trial site ends trial medication (as scheduled per protocol or prematurely). Individual Investigators will be notified of SUSARs occurring with the trial medication until 30 days after LPDD at their site.

Early termination of the trial is defined as the premature termination of the trial due to any reason before the end of the trial as specified in this protocol.

Temporary halt of the trial is defined as any unplanned interruption of the trial by the sponsor with the intention to resume it.

Suspension of the trial is defined as an interruption of the trial based on a Health Authority request.

10. APPENDICES

10.1 PHARMACOKINETIC ANALYSES

C_{max,ss} and t_{max,ss}: Individual C_{max} and t_{max} values will be directly determined from the plasma concentration time profiles of each subject. If the same C_{max,ss} concentration occurs at different time points, t_{max,ss} is assigned to the first occurrence of C_{max,ss}.

[REDACTED]

$$t_{1/2,ss} = \frac{\ln 2}{\lambda_z}$$

[REDACTED]

[REDACTED]

AUC: The area under the curve will be calculated using the linear up/log down algorithm. If an analyte concentration is equal to or higher than the preceding concentration, the linear trapezoidal method will be used. If the analyte concentration is smaller than the preceding concentration, the logarithmic method will be used.

Linear trapezoidal rule ($t_2 > t_1$ and $C_{t2} \geq C_{t1}$):

The area of the trapezoid between the two data points (t_1, C_{t1}) and (t_2, C_{t2}) will be computed by:

$$AUC_{t1-t2} = 0.5 \times (t_2 - t_1) \times (C_{t1} + C_{t2})$$

Logarithmic trapezoid rule ($t_2 > t_1$ and $C_{t2} < C_{t1}$):

The area of the trapezoid between the two data points (t_1, C_{t1}) and (t_2, C_{t2}) will be computed by:

$$AUC_{t1-t2} = \frac{(t_2 - t_1) \times (C_{t2} - C_{t1})}{\ln(C_{t2}/C_{t1})}$$

AUC_{0-∞}: The area under the plasma concentration-time curve over the time interval from 0 extrapolated to infinity will be calculated according to the following equation

$$AUC_{0-\infty} = AUC_{0-tz} + \frac{C'_{tz}}{\lambda_z}$$

where C'_{tz} is the concentration predicted by the regression line for the time t_z (time of last measurable concentration of the analyte in plasma). The area under the concentration-time curve over the time interval from 0 to the last quantifiable plasma concentration (AUC_{0-tz}) will be calculated by the linear up/log down method as described above.

%AUC_{tz-∞}: The percentage of the AUC_{0-∞} will be obtained by extrapolation according to the following equation:

$$\% \text{AUC}_{\text{tz-}\infty} = \frac{\text{AUC}_{0-\infty} - \text{AUC}_{0-\text{tz}}}{\text{AUC}_{0-\infty}} \times 100$$

[figure not shown]
[REDACTED]

$$\text{MRT}_{\text{po}} = \frac{\text{AUMC}_{0-\infty}}{\text{AUC}_{0-\infty}}$$

[REDACTED]

[figure not shown]
[REDACTED]

$$\text{AUMC}_{0-\infty} = \text{AUMC}_{0-\text{tz}} + \frac{C'_{\text{tz}} \times t_z}{\lambda_z} + \frac{C'_{\text{tz}}}{\lambda_z^2}$$

Proprietary confidential information © 2017 Boehringer Ingelheim International GmbH or one or more of its affiliated companies

$$\boxed{AUC} = \frac{\boxed{AUC}}{AUC_{0-\infty}}$$

$$CL_{R,t1-t2} = \frac{Ae_{t1-t2}}{AUC \boxed{AUC}}$$

gMean, gCV: The geometric mean (gMean) and coefficient of variation, gCV (given in %), will be calculated by the formulae:

$$\text{gMean} = \exp \left[\frac{1}{n} \sum_{i=1}^n \ln(x_i) \right] = \exp \left[\overline{\ln(x_i)} \right]$$

$$\text{gCV}(\%) = 100 \cdot \sqrt{\exp [\text{Var}(\ln(x_i))] - 1}$$

where

$$\text{Var}(\ln(x_i)) = \frac{1}{n-1} \sum_{i=1}^n \left[\ln(x_i) - \overline{\ln(x_i)} \right]^2$$

10.2 CLINICAL EVALUATION OF LIVER INJURY

10.2.1 Introduction

Alterations of liver laboratory parameters, as described in [Section 5.3.6.1](#) (Protocol-Specified Significant Events), are to be further evaluated using the following procedures:

10.2.2 Procedures

Repeat the following lab tests: ALT, AST, ALP and bilirubin (total and direct) - within 24 to 48 hours. If ALT and/or AST ≥ 3 fold ULN combined with an elevation of total bilirubin ≥ 2 fold ULN or an isolated elevation of AST and/or ALT ≥ 10 -fold ULN (without an elevation of total bilirubin ≥ 2 -fold ULN) are confirmed, results of the laboratory parameters described below must be made available to the investigator and to BI as soon as possible.

In addition,

- obtain a detailed history of current symptoms and concurrent diagnoses and medical history according to the “DILI checklist” provided in the ISF
- obtain history of concomitant drug use (including non-prescription medications, herbal and dietary supplement preparations), alcohol use, recreational drug use, and special diets according to the “DILI checklist” provided in the ISF;
- obtain a history of exposure to environmental chemical agents (consider home and work place exposure) according to the “DILI checklist” provided in the ISF; and report these via the CRF.

Clinical chemistry

alkaline phosphatase, albumin, prothrombin time (PT) or international normalised ratio, CK, CK-MB, ceruloplasmin, α -1 antitrypsin, transferin, amylase, lipase, FPG, cholesterol, triglycerides

Serology

Hepatitis A (Anti-IgM, Anti-IgG), Hepatitis B (HbsAg, Anti-HBs, DNA), Hepatitis C (Anti-HCV, RNA if Anti-HCV positive), Hepatitis D (Anti-IgM, Anti-IgG, if anti-IgM and anti-IgG are not available, total anti HepD can be performed), Hepatitis E (Anti- HEV), Anti-Smooth Muscle antibody (titer), Anti-nuclear antibody (titer), Anti-LKM (liver-kidney microsomes) antibody, Anti-mitochondrial antibody

Hormones, tumor marker

TSH

Haematology

Thrombocytes, eosinophils, complete blood count (including differential)

- Provide abdominal ultrasound to rule out biliary tract, pancreatic or intrahepatic pathology, e.g. bile duct stones or neoplasm.
- Initiate close observation of subjects by repeat testing of ALT, AST, and total bilirubin (with fractionation by total and direct) at least weekly until the laboratory ALT and / or AST abnormalities stabilize or return to normal, then according to the protocol. Depending on further laboratory changes, additional parameters identified e.g. by reflex testing will be followed up based on medical judgement and Good Clinical Practices (GCP).

[figure not shown]
11. DESCRIPTION OF GLOBAL AMENDMENTS

Number of global amendment	1
Date of CTP revision	17 Mar 2017
EudraCT number	Not applicable
BI Trial number	1321.6
BI Investigational Product(s)	Idarucizumab
Title of protocol	Open label Phase I trial in healthy Chinese male and female volunteers to investigate pharmacokinetics and pharmacodynamics of idarucizumab to reverse dabigatran anticoagulant activity
To be implemented only after approval of the IRB / IEC / Competent Authorities	
To be implemented immediately in order to eliminate hazard – IRB / IEC / Competent Authority to be notified of change with request for approval	
Can be implemented without IRB / IEC / Competent Authority approval as changes involve logistical or administrative aspects only	
Section to be changed	Flow Chart 1
Description of change	Deleted “X” sign of Blood sampling for PK of idarucizumab at day 1
Rationale for change	To keep the consistence between flow chart 1 and 2.
Section to be changed	Flow Chart 1
Description of change	Deleted The superscript 3 and 4 have been deleted for Laboratory / Urinalysis at day 11.
Rationale for change	To keep the consistence between flow chart 1 and 2.
Section to be changed	Flow Chart 2
Description of change	Deleted “X” sign of Physical examination at day 10(216 hours)

Rationale for change	To keep the consistence between flow chart 1 and 2.
Section to be changed	Section 3.3.4.1
Description of change	Deleted (except for serious adverse events (SAEs))
Rationale for change	Updates to reflect the updated AE reporting requirements
Section to be changed	Table 4.1.1.2
Description of change	3 days twice daily (b.i.d.) with a single dose on day 4 Was change to 3 days 220 mg twice daily (b.i.d.) with a single dose 220mg on day 4
Rationale for change	Provide more clear information about posology.
Section to be changed	Table 5.3.3:1
Description of change	Deleted Diff. Manual (if Diff. Automatic is abnormal)
Rationale for change	Diff Manual won't be conducted if Diff Automatic is abnormal
Section to be changed	Table 5.3.3:1
Description of change	Deleted Infectious Serology-and HIV-2
Rationale for change	Only HIV-1 antibody will be tested.
Section to be changed	Table 5.3.3:1
Description of change	Deleted Infectious Serology-RPR
Rationale for change	Only one type of method needs to be selected for syphilis test.
Section to be changed	Section 5.3.6.2

2. LIST OF ABBREVIATIONS

Term	Definition / description
ADA	Anti-drug antibodies
ADS	Analysis data set
AE	Adverse event
AESI	Adverse events of special interest
BI	Boehringer Ingelheim
CTP	Clinical Trial Protocol
CTR	Clinical Trial Report
DE	Dabigatran etexilate
dTT	Diluted thrombin time
ECG	Electrocardiogram
ETP	Endogenous Thrombin Potential
HR	Heart rate
ICH	International Conference on Harmonisation
MedDRA	Medical Dictionary for Regulatory Activities
O*C	Oracle Clinical
PD	Pharmacodynamics
PDS	Pharmacodynamic set
PK	Pharmacokinetics
PKS	Pharmacokinetic set
PR	Pulse rate
PV	Protocol violation
QT	Time between the start of the Q-wave and the end of the T-wave in an ECG
QT(c)	QT interval, any correction
QTcB	QT interval, corrected according to Bazett's formula
QTcF	QT interval, corrected according to Fridericia's formula
SD	Standard deviation

Proprietary confidential information © 2017 Boehringer Ingelheim International GmbH or one or more of its affiliated companies

Term	Definition / description
TSAP	Trial statistical analysis plan
WHO-DDE	World Health Organization Drug Dictionary Enhanced/Herbal

3. INTRODUCTION

As per International Conference on Harmonisation (ICH) E9, the purpose of this document is to provide a more technical and detailed elaboration of the principal features of the analysis described in the protocol, and to include detailed procedures for executing the statistical analysis of the primary and secondary variables and other data.

This trial statistical analysis plan (TSAP) assumes familiarity with the Clinical Trial Protocol (CTP), including Protocol Amendments. In particular, the TSAP is based on the planned analysis specification as written in CTP, Section 7 “Statistical Methods and Determination of Sample Size”. Therefore, TSAP readers may consult the CTP for more background information on the study, e.g., on study objectives, study design and population, treatments, definition of measurements and variables, planning of sample size, randomization.

SAS® Version 9.4 will be used for all analyses.

Pharmacokinetic (PK) and pharmacodynamic (PD) parameters will be calculated using WinNonlin™ software (professional Network version 6.3, Pharsight Corporation, Mountain View, CA 94041-1530, USA).

4. CHANGES IN THE PLANNED ANALYSIS OF THE STUDY

There has been no change in planned analyses from the statistical methods described in the CTP.

[figure not shown]
5. ENDPOINTS

5.1 PRIMARY ENDPOINT

The primary endpoints will be used as defined in the CTP, Section 5.1.1.

5.2 SECONDARY ENDPOINTS

The secondary endpoints will be used as defined in the CTP, Section 5.1.2.

5.4 OTHER VARIABLES

5.4.1 Demographic data and baseline characteristics

- Sex (Male, female)
- Age [years]
- Height [cm]
- Body weight [kg]
- Body mass index [kg/m²]
- Smoking status (Never smoked, Ex-smoker, Currently smokes)
- Alcohol status (Non-drinker, Drinks – no interference, Drinks - possibly interference)
- Medical history/baseline conditions
- Concomitant therapy

5.4.2 Safety data

The data used for safety assessment are specified in the CTP, Section 5.3.

6. GENERAL ANALYSIS DEFINITIONS

6.1 TREATMENT

The treatment regimens/study intervals with short label, sort order and start date/time included in the treatment set-up in Oracle Clinical (O*C) are described in the analysis data set (ADS) plan. Codes, decodes and sort order for treatment regimen included in the treatment set-up in O*C are described in the ADS plan. Detailed specifications are described in the ADS plan.

For safety analyses, the treatment assignment will be applied as defined in the CTP, Section 7.3.4. The data recorded prior to first intake of dabigatran will be assigned to 'screening', and those between first intake of dabigatran until first idarucizumab intake will be assigned to 'dabigatran period', and those between first intake of idarucizumab until the EOT visit will be assigned to 'dabigatran + treatment', and those between EOT visit until the end of trial (FU2 visit) will be assigned to 'post- treatment', and those after the end of trial visit examination will be assigned to 'post-study'.

6.2 IMPORTANT PROTOCOL VIOLATIONS

The [Table 6.2: 1](#) shows a list of all important protocol violations (PVs) since they may potentially affect the rights or safety of subjects. PVs are summarised into the following categories. They will be determined for entered subjects only. Exclusion of patients from analyses due to the PVs will be discussed at the final report planning meeting/the database lock meeting.

Table 6.2: 1 Important PVs

Category/Code	Description	Example/Comment	Excluded from	Program/Manual
A	Entrance criteria not met			
	A1 Inclusion criteria not met			
	A1.1 age<18 or age>45 years	IN1 not met.	None	Program + Manual
	A1.2 Heathy volunteer criteria not met	IN2 not met.	None	Program + Manual
	A1.3 Weight <50 kg or (BMI<19.0 or BMI \geq 24.0 kg/m ²)	IN3 not met.	None	Program + Manual
	A2 Exclusion criteria violated	Exclusion criteria not met as specified in the protocol.	None	Program + Manual
B	Informed consent			
	B1 Informed consent not available/not done	IN4 not met.	All	Program + Manual
	B2 Informed consent too late	Informed consent date was after Visit 1 date.	None	Program + Manual
C	Trial medication and randomisation			
	C1 Incorrect trial medication taken	Wrong medication	None	Manual
D	Concomitant medication			
	D1 Prohibited medication use	Prohibited medication	None	Manual

6.3 PATIENT SETS ANALYSED

All analyses will be based on the treated set.

- Treated set (TS):
This subject set includes all subjects who received the idarucizumab.
- Pharmacokinetic set (PKS):
This subject set includes all subjects who received the idarucizumab and who had at least one PK parameter.
- Pharmacodynamic set (PDS):
This subject set includes all subjects in the TS who provide at least one evaluable predose and/or one on-treatment PD observation after the start of administration of dabigatran. This analysis set is used for all PD analyses.

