[figure not shown]
[figure not shown]
[figure not shown]

CLINICAL TRIAL PROTOCOL

Document Number:		c02286986-03
BI Trial No.:	1321.6	
BI Investigational Products:	Idarucizumab	
Title:	Open label Phase I trial in healthy Chinese male and female volunteers to investigate pharmacokinetics and pharmacodynamics of idarucizumab to reverse dabigatran anticoagulant activity	
Lay Title:	Study to evaluate the safety, pharmacokinetics and pharmacodynamics of idarucizumab (BI 655075) administered alone or with dabigatran etexilate in Chinese healthy subjects	
Clinical Phase:	I	
Trial Clinical Monitor:	 Phone:  Fax: 	
Principal Investigator :	 Phone:  Fax: 	
Status:	Final Protocol (Revised protocol (based on global amendment 1))	
Version and Date:	Version: 2.0	Date: 17 Mar 2017
Page 1 of 98		
<small>Proprietary confidential information. © 2017 Boehringer Ingelheim International GmbH or one or more of its affiliated companies. All rights reserved. This document may not - in full or in part - be passed on, reproduced, published or otherwise used without prior written permission</small>		

CLINICAL TRIAL PROTOCOL SYNOPSIS

Name of company:		Boehringer Ingelheim	
Name of finished product:		Not Applicable	
Name of active ingredient:		Idarucizumab	
Protocol date: 20 Oct 2016	Trial number: 1321.6		Revision date: 17 Mar 2017
Title of trial:	Open label Phase I trial in healthy Chinese male and female volunteers to investigate pharmacokinetics and pharmacodynamics of idarucizumab to reverse dabigatran anticoagulant activity		
Principal Investigator:			
Trial sites:	Single centre [REDACTED]		
Clinical phase:	I		
Objectives:	To investigate pharmacokinetic and pharmacodynamic of idarucizumab administered at or close to the steady state of dabigatran		
Methodology:	Open label, single centre		
No. of patients:	12		
total entered:	12		
each treatment:	12 subjects (approximately sex ratio: 1:1)		
Diagnosis :	Not Applicable		
Main criteria for inclusion:	age \geq 18 and \leq 45 years, Body weight \geq 50 kg , BMI range: \geq 19 and $<$ 24 kg/m ²		
Test products:	a) Idarucizumab (50 mg/mL in buffer solution for infusion) b) Dabigatran etexilate (110 mg capsules); only as NIMP		
dose:	a) 2 short infusions of 2500 mg each 15minutes apart administered at or close to the steady state of dabigatran; b) 220 mg b.i.d		

Name of company:	Boehringer Ingelheim	
Name of finished product:	Not Applicable	
Name of active ingredient:	Idarucizumab	

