3. DESCRIPTION OF DESIGN AND TRIAL POPULATION

3.1 OVERALL TRIAL DESIGN AND PLAN

This trial will be open label with only 1 dose group.

A total of 12 subjects will participate in the trial.

This trial consists of two periods; the dabigatran etexilate administration alone period is intended to evaluate the safety of multiple doses of 220 mg dabigatran etexilate b.i.d, and in the second period idarucizumab will be administered at or close to steady state of dabigatran and is intended for exploratory PK/PD analysis with the dose (2500 mg followed by 2500 mg).

At the dabigatran etexilate administration alone period, all subjects will receive 220 mg dabigatran etexilate b.i.d. (440 mg daily dose) for 3 days and a single 220 mg dose on day 4 to reach dabigatran or close to steady state.

Following dabigatran etexilate administration alone, after a washout period of 3 days and evaluation of safety 220 mg dabigatran etexilate will be administered twice daily over 3 days (from day 8 to day 10) with a single 220 mg dose on day 11. The dose of idarucizumab (2500 mg followed by 2500 mg is planned) will be administered intravenously approximately 2 hours after the last dabigatran administration.

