7.3 PLANNED ANALYSES

All statistical analyses will be based on the treated set.

Treated set:

This subject set includes all subjects who received the investigational drug.

When necessary, PK/PD set may be created for PK/PD analysis, details will be described in the TSAP.

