7. PLANNED ANALYSIS

For End-Of-Text tables for non-PK parameters, the set of summary statistics is: N / Mean / SD / Min / Median / Max.

Tabulations of frequencies for categorical data will include all possible categories and will display the number of observations in a category as well as the percentage (%) relative to the respective treatment group (unless otherwise specified, all subjects in the respective subject set whether they have non-missing values or not). Percentages will be rounded to one decimal place. The category missing will be displayed only if there are actually missing values.

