7.8 SAFETY ANALYSIS

All safety analyses will be performed on the treated set.

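### Every safety table is restricted to subjects who received idarucizumab, so a subject who stops during dabigatran dosing is missing from the 'dabigatran period' tables

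*SAP*

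**What the plan says.** SAP 6.3 bases all analyses on the treated set and defines it: "This subject set includes all subjects who received the idarucizumab". SAP 7.8 repeats this for safety: "All safety analyses will be performed on the treated set". SAP 7 takes percentages over "all subjects in the respective subject set whether they have non-missing values or not". No separate safety set is defined.

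Protocol 7.3 words the treated set differently: "This subject set includes all subjects who received the investigational drug". The effect is the same, because the protocol synopsis lists the other drug as "Dabigatran etexilate (110 mg capsules); only as NIMP", so a dabigatran dose does not qualify a subject.

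SAP 6.1, following protocol 7.3.4, nevertheless sets up a reporting interval that lies wholly before idarucizumab: "those between first intake of dabigatran until first idarucizumab intake will be assigned to" the 'dabigatran period'. Protocol 3.1 gives the first part of that interval a purpose: "the dabigatran etexilate administration alone period is intended to evaluate the safety of multiple doses of 220 mg dabigatran etexilate b.i.d". Protocol 2.3 says the same and adds tolerability. SAP 4 states: "There has been no change in planned analyses from the statistical methods described in the CTP".

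**The concern.** Membership of the set used to describe dabigatran safety depends on something that happens after the dabigatran period, namely the Day 11 infusion. A subject who takes dabigatran etexilate and leaves before then appears in no planned safety table, whatever happened to that subject.

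The omission can be selective. Protocol 4.2.1 stops trial medication for a major bleed. Protocol 3.3.4.2 names clinically relevant bleeding and sufficiently severe adverse events among the reasons to discontinue. Protocol 3.3.4.1 allows replacement, which can bring the treated set back to 12 so that the tables show no sign of a loss.

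At stake is the descriptive adverse event incidence for the dabigatran period. SAP 7.8.1 also plans a table of other significant events, which includes events leading to discontinuation. On the present set, a subject whose event ends participation before Day 11 cannot be counted there.

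**Working it through.** The plan gives no figure to reproduce: protocol 7.7 says that the 12 subjects do not come from a power calculation. The check is a comparison of definitions, followed by an illustration of size.

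**Step 1: exposure before the first infusion.** Protocol 6.2.2 gives twice-daily dosing on Days 1 to 3 with one dose on Day 4, then the same on Days 8 to 10 with one dose on Day 11. Idarucizumab starts about 1 hour 55 minutes after the last dose.

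Doses before idarucizumab = 2 × (3 × 2 + 1) = 14.

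**Step 2: status of a subject who stops before the infusion.**

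- Took dabigatran etexilate: yes, so the subject has data in the 'dabigatran period' (SAP 6.1).
- Received idarucizumab: no, so the subject is outside the treated set (SAP 6.3; protocol 7.3 has the same effect).
- Safety tables use the treated set (SAP 7.8), and percentages are taken over the subject set (SAP 7). The subject is therefore in neither numerator nor denominator.

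**Step 3: effect on a table.** Assume that one dabigatran-exposed subject has a bleed and stops before Day 11, and that no other subject has that event. Intervals are exact Clopper-Pearson 95%. With zero events the upper limit is 1 − 0.025^(1/n).

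| Assumption | Table as planned | All dabigatran-exposed subjects |
|---|---|---|
| Stopper replaced | 0/12 = 0% (0 to 26.5%) | 1/13 = 7.7% (0.2 to 36.0%) |
| Stopper not replaced | 0/11 = 0% (0 to 28.5%) | 1/12 = 8.3% (0.2 to 38.5%) |
| Two such stoppers, not replaced | 0/10 = 0% | 2/12 = 16.7% |

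**Step 4: how often the set definition would matter.** The documents give no dropout rate, so the per-subject risk p of stopping before idarucizumab, for any reason, is assumed. The chance of at least one stop among 12 is 1 − (1 − p)^12:

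- p = 1%: 1 − 0.99^12 = 11%
- p = 2%: 1 − 0.98^12 = 22%
- p = 5%: 1 − 0.95^12 = 46%

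These are chances that the set excludes someone. They are not chances of a hidden bleed, which needs a stop by a subject who had the event.

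**The case against.** The strongest case for leaving the plan alone has five parts.

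- **The effect is conditional.** These are screened healthy volunteers, dosed under supervision in-house. Protocol 2.3 rates severe adverse events as very unlikely, and protocol 4.2.1 favours observation for minor bleeding. This stands: most minor bleeds would not remove a subject, and a subject who bleeds but is still infused is counted.
- **The bias is not always downward.** A subject who leaves without an event and is not replaced shrinks the denominator and raises the rate (for example 1/11 = 9.1% instead of 1/12 = 8.3%). This also stands. The downward bias applies to stops caused by the event being tabulated.
- **The safety purpose in protocol 3.1 belongs to the first course**; the second is described as exploratory PK/PD. This is a fair reading, and it means that 7 of the 14 doses carry the stated safety aim. Subjects who stop in the first course or the washout are still omitted.
- **The events will be seen anyway.** Protocol 3.3.4.1 requires withdrawn subjects' data to be reported and the withdrawals discussed, and SAP 7.8.1 lists subjects with serious or other significant events. The first part stands. The SAP listings fall under SAP 7.8 and so, as written, under the same treated set. A narrative also does not correct a table that reads 0%.
- **SAP and protocol agree, and nothing is tested.** Both are true, and the statement in SAP 4 is accurate on this point today. Agreement between the two definitions does not reconcile either of them with the stated safety purpose, and descriptive tables are the trial's planned output (protocol 7.2).

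**Conclusion.** The concern holds. As written, a subject who takes dabigatran etexilate but does not reach the Day 11 infusion is left out of every planned safety table, including those for the period in which that subject was exposed. When the stop is due to an adverse event, the tabulated incidence of that event is too low; with about 12 subjects, one omission moves it by roughly 8 percentage points (7.7 or 8.3, depending on replacement). This rests on an assumed early stop, since the documents give no rate, and the effect is zero if everyone is infused. The tables are descriptive and are not primary or secondary endpoints, and the data remain in the database and the report. It should be fixed, because an analysis set has to be right before it is known who stops.

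**What to change.** - **SAP 6.3:** add a safety set of all subjects with at least one dose of dabigatran etexilate or idarucizumab. Keep the idarucizumab-based set for PK and PD.
- **SAP 7.8:** use the safety set and state the denominators, since SAP 7 otherwise defaults to the whole set. Use all dabigatran-dosed subjects for the 'dabigatran period' and idarucizumab-dosed subjects from the first infusion onward.
- **SAP 6.1:** say where the 'dabigatran period' ends for a subject who never receives idarucizumab, for example at the end-of-treatment evaluation that protocol 3.3.4.1 calls for at discontinuation. At present the interval closes only at first idarucizumab intake.
- **SAP 4:** declare the departure from protocol 7.3, and align protocol 7.3 if it is amended.

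The cost is wording in four SAP sections and minor programming of the period-specific denominators. No new data are needed, and no dosing or stopping rule is touched. Dabigatran-period rates may look slightly less favourable.
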